3.2. Study Treatment

In Part 1

Participants with ALS:

Cohort A: BIIB105 5 mg or placebo

Cohort B: BIIB105 20 mg or placebo

Cohort C1: BIIB105 60 mg or placebo

Cohort D1: BIIB105 120 mg or placebo

Participants with polyQ-ALS:

Cohort C2: BIIB105 60 mg or placebo

Cohort D2: BIIB105 120 mg or placebo

Participants in Cohorts A, B, C1, and C2 will receive 3 loading doses administered every 2 weeks (on Days 1, 15, and 29), followed by 2 maintenance doses administered once every 4 weeks (on Days 57 and 85), for a total of 5 doses over approximately 13 weeks.

Participants in Cohorts D1 and D2 will receive 3 loading doses administered every 2 weeks (on Days 1, 15, and 29), followed by 5 maintenance doses administered once every 4 weeks (on Days 57, 85, 113, 141, and 169), for a total of 8 doses over approximately 25 weeks.

In Part 2:

Participants will receive up to approximately 41 doses in Part 2. Two dose levels will be administered – participants from Part 1 Cohorts A, B, C1, and C2 will receive 60 mg BIIB105; participants from Part 1 Cohorts D1 and D2 will receive 120 mg BIIB105.

In Part 2, the 60 mg dose may be increased, based on Sponsor review of emerging safety, PK, PD, and/or clinical data from the study, to doses up to 120 mg. The 60 mg dose in Part 2 was increased to 120 mg following the SST review on 13 December 2023. Doses in Part 2 may also be decreased, based on Sponsor review of emerging safety, PK, PD, and/or clinical data from the study.

CONFIDENTIAL

The information contained herein may not be used, disclosed, or published without the written consent of
Biogen MA Inc.

3.3. Subgroup Variable

As no notable difference was observed across all efficacy/safety endpoints in interim analyses, no subgroup analyses are planned for final CSR.

3.4. Analysis Sets

Part 1

1) Part 1 FAS Population

The Part 1 FAS population is defined as all randomized participants who received at least 1 dose of study treatment in Part 1. In analyses performed on the FAS, participants will be analyzed, based on the intent-to-treat (ITT) principle, according to their randomized treatment assignment regardless of treatment received.

2) Part 1 Safety Analysis Population

The Part 1 safety analysis population is defined as all randomized participants who received at least 1 dose of study treatment in Part 1. In the case of any subjects who are mis-randomized, then any analyses based on the safety analysis population will be based on actual treatment received.

3) Part 1 PK Analysis Population

The Part 1 PK analysis population is defined as all randomized participants who received at least 1 dose of study treatment and have at least 1 postdose serum and/or CSF BIIB105 measurement in Part 1.

4) Part 1 PD Population

The Part 1 PD population is defined as subjects who received at least 1 dose of study treatment and have at least 1 available postdose evaluation of the respective PD endpoint in the study in Part 1.

5) Part 1 Clinical Function Population

The Part 1 clinical function population is defined as the subset of the FAS population who have at least 1 postdose measurement in Part 1.

Part 2

1) Part 2 FAS Population

The Part 2 FAS population is defined as all enrolled participants who received at least 1 dose of study treatment in Part 2.

2) Part 2 Safety Analysis Population

The Part 2 safety analysis population is defined as all participants who received at least 1 dose of study treatment in Part 2.

Integrated Part 1 and Part 2

Integrated data for Part 1 and Part 2 will be analyzed based on the following populations defined for Part 1, with the exception of the safety data, which will be defined separately:

CONFIDENTIAL

The information contained herein may not be used, disclosed, or published without the written consent of
Biogen MA Inc.

Part 1 FAS population, Part 1 PK population, Part 1 PD population, and Part 1 clinical function population.

The Integrated Part 1 and Part 2 safety analysis population is defined as all randomized participants who received at least 1 dose of BIIB105 either in Part 1 or Part 2.

3.5. Treatment Group

In the integrated safety and PK summary of Part 1 and Part 2, summaries and analyses will be presented by treatment received for the subjects in the safety population defined previously. The following treatment group will be considered for the safety data:

- BIIB105 Pool 120 mg DL: this group includes Cohorts D1 and D2 participants who received at least one dose of BIIB105 120 mg in Part 1 or Part 2, i.e. total of all subjects in Part 1 Cohorts D1 and D2 exposed to BIIB105 120 mg during Part 1 (i.e. DL1) or initiated during Part 2 (DL2). Data since their first dose of BIIB105 120 mg will be included.
- BIIB105 Pool 60 mg: this group includes the participants who received at least one dose of BIIB105 60 mg in Part 1 or Part 2. The 60 mg dose in Part 2 was increased to 120 mg starting December 2023. Data since their first dose of BIIB105 60 mg and before their first dose of 120 mg will be included in analysis for this pool. Baseline is defined as first dose of BIIB105 60 mg.
- BIIB105 Pool 120 mg: this group includes the participants who received at least one dose of BIIB105 120 mg in Part 1 or Part 2. Data since their first dose of BIIB105 120 mg will be included. Baseline is defined as first dose of BIIB105 120 mg. In addition to participants from BIIB105 Pool 120 mg DL, this group will also include Cohort A, B, C1, and C2 participants who received at least one dose of BIIB105 120 mg in Part 2, i.e. participants escalated from 60 mg to 120 mg in Part 2.

In the integrated efficacy and biomarker summary of Part 1 and Part 2 for D1 and D2, pooled group “DL” includes cohorts D1 and D2 subjects in Part 1 clinical function population or PD population and data since their first dose of study drug treatment in Part 1 will be included. The following treatment group will be considered for the efficacy data:

- Placebo/Delayed-start BIIB105 120 mg: this group includes the Cohorts D1 and D2 subjects in the Part 1 FAS population who were on placebo in Part 1, who may or may not roll over to Part 2 and start active treatment with BIIB105. Data since their first dose of study drug treatment in Part 1 will be included. Baseline is defined as the Day 1 of Part 1.
- Early-start BIIB105 120 mg: this group includes the Cohorts D1 and D2 subjects in the Part 1 FAS population who were on BIIB105 120 mg in Part 1, who may or may not continue their study treatment in Part 2. Data since their first dose of 120 mg in Part 1 will be included. Baseline is defined as the Day 1 of Part 1.

CONFIDENTIAL

The information contained herein may not be used, disclosed, or published without the written consent of
Biogen MA Inc.

4. List of Planned Study Analyses

4.1. Interim Analysis

An interim analysis of unblinded key safety, secondary, [REDACTED] endpoints (including PK, PD, clinical function) for Part 2 and integrated analyses of Part 1 and Part 2 was conducted following the completion of Day 175/176 visit for all Part 1 subjects to inform decisions on the BIIB105 clinical development program, the database lock date was April 29, 2024.

4.2. End of Long-term Follow-up Analysis

As the study is early terminated by sponsor, analysis of key safety, secondary, [REDACTED] endpoints (including PK, PD, clinical function) for Part 2 and integrated analysis of Part 1 and Part 2 will be conducted.

5. Statistical Methods for Planned Analyses

5.1. General Principles

Descriptive summary statistics will be presented for all primary, secondary, and [REDACTED] endpoints collected. Unless otherwise specified, for continuous endpoints, the summary statistics will generally include number of subjects with data, mean, standard deviation, median, first and third quantiles and range. For categorical endpoints, the summary statistics will generally include number of subjects with data, and frequent counts the percentage of those with data in each category.

As a general rule, any visit/dose group combination that only has data for 1 participant will not be presented in group plots. All data will be listed, unless otherwise specified.

The statistical software, SAS® Version 9.4 or above, will be used for all summaries and statistical analyses.

5.2. Participant Accountability

Analyses in this section will be analyzed for Part 2 FAS population and integrated Part 1 and Part 2 FAS population. For Part 2, the summaries will be presented by initial dose level in Part 2 (BIIB105 60 mg vs BIIB105 120 mg), and for all subjects combined. Selected summaries for Part 2 Cohorts D1+D2 may also be summarized by treatment assignment in Part 1 (120 mg [Cohorts D1+D2] and Placebo [Cohorts D1+D2]). For integrated Part 1 and Part 2, the summaries will be presented by treatment assignment in Part 1 for subjects in Cohorts D1 and D2.

For Part 2, the number (and percentage) of subjects dosed; completed the treatment; completed the study; completed the study but missed one or more doses; discontinued treatment and the reasons for discontinuation; and withdrew from study early and the reasons for withdrawal will be summarized in a table. The number of subjects who enrolled and completed study will be summarized.

For integrated Part 1 and Part 2, number (and percentage) of subjects dosed in Part 1, dosed in Part 2, ongoing in Part 1 at interim, ongoing in Part 2 at interim, died in Part 1, died in Part

CONFIDENTIAL

The information contained herein may not be used, disclosed, or published without the written consent of
Biogen MA Inc.

2, discontinued treatment and reasons for discontinuation, and withdrew from study early and the reasons for withdrawal will be summarized in a table.

A listing of subjects who discontinued treatment/withdrew from study and the associated reasons for discontinuation/withdrawal will be presented.

5.3. Medical History

A summary of medical history will be presented for Part 2 by initial dose level in Part 2. Medical history will be classified using MedDRA version 24.1 or later if available. A summary of medical history by system organ class and preferred term will also be provided.

5.4. Protocol Deviations

For Part 2, protocol deviations identified during site monitoring will be captured in a protocol deviation log. All protocol deviations will be listed and a summary of major protocol deviations by initial dose level in Part 2 will also be provided. For subjects who escalate from 60 mg to 120 mg in Part 2, protocol deviations after their first dose of escalation to 120 mg will be summarized separately.

5.5. Study Treatment Exposure and Concomitant Medications and Non-Drug Treatments/Procedures

Extent of exposure to study treatment will be summarized for Part 2 by initial dose level. Number of participants who received BIIB105 60 mg or BIIB105 120 mg in Part 2 will be summarized by initial dose, as well as total cumulative dose in mg.

Study drug compliance percentage up to the last dose of study drug received in Part 2 will be defined as the number of doses actually received divided by the number of doses that the subject is expected to receive during the Part 2 study period and will be summarized descriptively and categorically (<80%, 80%-90%, 90%-100%). For participants who withdrew from Part 2 early, the number of expected doses is the planned number of doses before the time of withdrawal.

Duration of exposure and time on study will be summarized descriptively by initial dose. Duration of exposure will be calculated as (last dose date – first dose date +1) in days and time on study will be calculated as (end of study date – first dose date +1) in days.

Concomitant Medications and non-drug treatment/procedures will be analyzed for Part 2 by initial dose level. For subjects who escalate from 60 mg to 120 mg in Part 2, concomitant medications and non-drug treatments/procedure with start date after their first dose of escalation to 120 mg will be summarized separately.

Concomitant medications will be coded using the World Health Organization (WHO) dictionary WHODRUG (Mar 2024) and concomitant non-drug treatments/procedures using the Medical Dictionary for Regulatory Activities (MedDRA) version 24.1 or later if available.

Medications and non-drug treatments are considered concomitant if they are taken during the study. This includes medications/treatment/procedures that were started prior to the date and

CONFIDENTIAL

The information contained herein may not be used, disclosed, or published without the written consent of
Biogen MA Inc.

time of first dose of study drug if their use continued on or after the date and time of first dosing. If the start date is available but start time is missing and the medication/non-drug treatment start date is the same as the first dose date, the medication/non-drug treatment will be considered concomitant. Similarly, if the stop date is available but stop time is missing and the medication/non-drug treatment stop date is the same as the first dose date, the medication/non-drug treatment will also be considered concomitant. Medications/therapies with missing start or stop dates and times, will also be considered as concomitant in the following situations:

- If both the start and stop dates and times of a medication/treatment/procedure are missing.
- If the start date and time of a medication/treatment/procedure is missing and the stop date and time of the medication/therapy occurred on or after the date and time of first dose of study drug.
- If the start date and time of a medication/treatment/procedure therapy occurred prior to the date and time of first dose of study drug and the stop date and time of the medication/treatment/procedure is missing and the medication/treatment/procedure is listed as ongoing.

If the start date and time of a medication/treatment/procedure occurred prior to the date and time of first dose of study drug and the stop date and time of the medication/treatment/procedure is missing and the medication/therapy is not listed as ongoing, then the medication/treatment/procedure will be considered as concomitant.

The number and percentage of subjects taking any concomitant medications will be summarized for the safety population. The number and percentage of subjects taking any concomitant non-drug treatments and disallowed concomitant medications will also be summarized for the safety population.

5.6. Efficacy Endpoints

5.6.1. General Analysis Methods for Efficacy Endpoints

Covariates

The covariates for the statistical models in the integrated analysis for participants from Cohorts D1 and D2 will be based on Part 1 baseline and will be as follows:

- Corresponding baseline score for the endpoint (continuous)
- Baseline disease duration from onset of symptoms to the first dose of study treatment as derived in Appendix 1, i.e. time since symptom onset in months (continuous)
- Baseline plasma NfL
- Riluzole or Edaravone use which will take 3 levels as follows:
 - Edaravone Use (Edaravone = Yes; Riluzole = Yes OR No)
 - Riluzole Only (Riluzole = Yes and Edaravone = No)

CONFIDENTIAL

The information contained herein may not be used, disclosed, or published without the written consent of Biogen MA Inc.

- Neither (Edaravone = No and Riluzole = No)

Edaravone use may only occur for a very small number of subjects in which case this could cause problems for statistical modelling. If Edaravone use is limited to <5 subjects within the relevant population then riluzole and edaravone use will be combined so that there are only 2 levels:

- Edaravone or Riluzole Use (Edaravone = Yes and Riluzole = Yes; OR Edaravone = Yes and Riluzole = No; OR Edaravone = No and Riluzole=Yes)
- Neither (Edaravone = No and Riluzole = No)

Missing data for individual items in scales

The imputation of individual components of each endpoint are described in Section 5.6.2. Imputation will be performed within a scale for each endpoint by prorating the observed scores at the same visit, for example, if there are missing responses to some of the individual questions on a scale at a given visit the endpoint may only be derived for that visit if there are a certain number of individual items/components with available data. Specific details are provided for each assessment/scale, as this differs across assessments/scales. These imputations within a visit will be performed prior to applying imputations on the endpoint at the visit level (e.g. multiple imputation) and will be applied consistently across visits where required. Multiple imputation will not be applied on an individual item/question within an assessment/scale.

Multiple imputation (MI)

Missing data for postbaseline assessments will be imputed using the multiple imputation method [Schafer 1997, Schafer 1999]. Visit windowing as described in Section 4.5 will be applied prior to any imputations. Any imputation on an item level within a scale will be performed prior to performing MI.

MI will be performed on actual values, domains, total scores or summary scores depending on the endpoint and not performed at the item level; the complete datasets can then be used to calculate change from baseline.

All available data will be used where subjects have missed doses but continued to perform assessments; otherwise any missing values will be imputed using MI. The Markov Chain Monte Carlo (MCMC) will be used to impute the missing postbaseline scores in the endpoint by treatment group.

Prior to performing multiple imputation, the dataset will be sorted by ascending unique subject identifier (USUBJID). The treatment variable will be coded so that early-start BIIB105 120 mg is set to 0 and placebo/delayed-start BIIB105 120 mg is set to 1 for inclusion in the MI model. Similarly, two level riluzole/edaravone use will be set to 0 for

CONFIDENTIAL

The information contained herein may not be used, disclosed, or published without the written consent of
Biogen MA Inc.

no use (i.e. neither riluzole or edaravone) and 1 for use of either riluzole or edaravone or both. When three level riluzole/edaravone use is used, two binary variables (edaril3cat1 and edaril3cat2) will be coded, where both variables will be set to 0 for no use (i.e. neither riluzole or edaravone), edaril3cat1 is set to 1 and edaril3cat2 is set to 0 for use of riluzole only, and edaril3cat1 is set to 0 and edaril3cat2 is set to 1 for edaravone use. The variable list in the model for imputations will include treatment group, riluzole/edaravone use, the corresponding baseline value for the endpoint, and all available postbaseline values. The MI model will be performed by treatment group. A set of 100 complete imputed datasets will be generated. This number of imputed datasets needs to be large enough for applying the multiple imputation method in this study as the sample size is small. The relative efficiency parameter will also be checked to determine the acceptability of the imputed results i.e. it should be close to 98% or higher. The seed used for the multiple imputation is specified in [Table 2](#).

Table 2: Seed used for each endpoint in MI

Endpoint	Seed
ALSFRS-R Bulbar function Respiratory function Fine motor skills Gross motor skills (Total score will not be imputed separately; instead the imputed datasets from the functional domains will be used to calculate the total score. A separate model will be used for each functional domain.)	8492382
Percent predicted SVC	6734934
HHD megascore (overall, upper extremities, lower extremities)	3748311
[REDACTED]	[REDACTED]
[REDACTED] [REDACTED] [REDACTED]	[REDACTED]
[REDACTED]	[REDACTED]

Imputed values that are outside of the expected range of a scale will be reset: for example, for ALSFRS-R bulbar function should only be in the range 0 to 12. Values outside of this

CONFIDENTIAL

The information contained herein may not be used, disclosed, or published without the written consent of
Biogen MA Inc.

range will be reset so that values below 0 are set to 0 and values above 12 are set to 12. Values will be used as imputed, and will not be rounded prior to analysis.

For each of the 100 imputed datasets, change from baseline will be calculated using the imputed datasets, and the change from baseline endpoint will be compared between treatment groups using an ANCOVA model for continuous endpoints (efficacy and pharmacodynamic endpoints). The ANCOVA model will include covariates for each of the corresponding baseline value for the endpoint, baseline plasma NfL, baseline disease duration since symptom onset, and use of riluzole or edaravone. The model will be used to present overall LS means and standard errors for each treatment group, and LS mean differences for treatment with corresponding 95% CI and p-values. A combined estimate of the LS means, LS mean differences and standard errors of the 100 imputed datasets will be obtained, where standard errors will be used to obtain 95% CI from PROC MIANALYZE [Little et al, 2002]. Separate ANCOVA models will be used to obtain estimates, 95% confidence intervals and p-values for other visits. For subjects who died, the imputed values after death will be used in the ANCOVA analysis eg change from baseline in ALSFRS-R.

For integrated analyses of Part 1 and Part 2 for Cohorts D1 and D2, ANCOVA model will be performed for Early-start BIIB105 120 mg vs. Placebo/Delayed-start BIIB105 120 mg.

Presentation of Data

The actual scores and changes from baseline in each measure will be summarized using descriptive statistics. Missing data will be imputed using multiple imputation. Multiple imputation will be performed on actual values, domains, total scores, or summary scores depending on the endpoint. In addition, each clinical function measure will be analyzed using an ANCOVA model. The model may include covariates such as corresponding baseline value, baseline NfL, duration from onset of symptoms to the first dose of study treatment, broad ALS/polyQ ALS, and riluzole or edaravone use. The model will be used to estimate least-square (LS) means for each treatment group with standard errors (SEs), and LS mean differences between treatment groups with corresponding 95% confidence intervals (CIs). The p-values comparing treatment differences will also be presented. LS mean changes over time will be also presented in line plots.

For integrated analyses of Part 1 and Part 2 for Cohorts D1 and D2, treatment groups will be defined as Early-start BIIB105 120 mg (i.e., those who initiated BIIB105 120 mg in Part 1) and Placebo/Delayed-start BIIB105 120 mg (i.e., those who received placebo in Part 1), with baseline defined as Part 1 baseline. Clinical function data will be presented by treatment group (Early-Start BIIB105 120 mg vs Placebo/Delayed-start BIIB105 120 mg). They might also be presented by cohort and treatment group as a sensitivity analysis (Cohort D1 Early-start vs Placebo/Delayed-start; Cohort D2 Early-start vs. Placebo/Delayed-start).

CONFIDENTIAL

The information contained herein may not be used, disclosed, or published without the written consent of
Biogen MA Inc.

Due to the washout period between Part 1 and Part 2 for all participants in Cohorts A, B, C1, and C2, Part 2 clinical function data for these cohorts will be presented separately from Part 1. Descriptive summaries will be presented for the combined cohort (A+B+C1+C2) by their initial dose level, i.e. 60 mg in Part 2 with baseline defined as Part 2 baseline. As participants on the 60 mg dose in Part 2 were increased to 120 mg starting December 2023, visits since first dose escalation to 120 mg will not be included in the analysis for Part 2 BIIB105 60 mg.

CONFIDENTIAL

The information contained herein may not be used, disclosed, or published without the written consent of
Biogen MA Inc.

Table 3: Analysis Methods for Part 2 and Integrated Summary of Efficacy and PD Data

Endpoint	Summary/ Analysis	Part 2	Integrated Part 1 and Part 2
		BIIB105 60 mg	Pool DL (Placebo/delayed-start BIIB105 120 mg And Early-start BIIB105 120 mg)
Absolute value/change in ALSFRS-R total score since Part 1 baseline	Observed data all visits descriptive		x
Absolute value/change in ALSFRS-R total score since Part 2 baseline	Observed data all visits descriptive	x	
Change in ALSFRS-R total score by selected time points since Part 1 baseline	MI data + ANCOVA		x
Absolute value/change in percent predicted SVC since Part 1 baseline	Observed data all visits descriptive		x
Absolute value/change in percent predicted SVC since Part 2 baseline	Observed data all visits descriptive	x	
Change in percent predicted SVC by selected time points since Part 1 baseline	MI data + ANCOVA		x
Absolute value/change in HHD megascore since Part 1 baseline	Observed data all visits descriptive		x
Absolute value/change in HHD megascore since Part 2 baseline	Observed data all visits descriptive	x	
Change in HHD megascore by selected	MI data + ANCOVA		x

CONFIDENTIAL

The information contained herein may not be used, disclosed, or published without the written consent of
Biogen MA Inc.

time points since Part 1 baseline			
Time to event endpoints since Part 1 baseline	K-M plot Cox model		x

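### The imputation model for ALSFRS-R, SVC and HHD omits two ANCOVA covariates, baseline NfL and time since onset; this can bias arm means and, if NfL-related drop-out differs by arm, the Week 40 contrast

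*SAP*

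**What the plan says.** All references are to the Part 2/integrated SAP unless stated otherwise.

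- **Imputation model (5.6.1, Multiple imputation).** The list opens: "The variable list in the model for imputations will include treatment group, riluzole/edaravone use, the corresponding baseline value for the endpoint". Its last item is the set of observed post-baseline scores, and the next sentence calls for a separate run in each arm. The by-arm instruction also appears earlier in the section: "The Markov Chain Monte Carlo (MCMC) will be used to impute the missing postbaseline scores in the endpoint by treatment group". On the number of imputations: "A set of 100 complete imputed datasets will be generated".
- **Analysis model (5.6.1, same subsection).** "The ANCOVA model will include covariates for each of the corresponding baseline value for the endpoint, baseline plasma NfL, baseline disease duration since symptom onset", together with riluzole or edaravone use. The Covariates list at the start of 5.6.1 names baseline plasma NfL, and also: "Baseline disease duration from onset of symptoms to the first dose of study treatment as derived in Appendix 1".
- **Second covariate list (5.6.1, Presentation of Data).** This list is optional and includes "duration from onset of symptoms to the first dose of study treatment, broad ALS/polyQ ALS, and riluzole or edaravone use".
- **Where it is used.** Sections 5.6.2 (ALSFRS-R), 5.6.3 (HHD) and 5.6.4 (SVC) each take the Week 40 difference, Early-start versus Placebo/Delayed-start, from this imputation and ANCOVA.
- **Numbers.** Protocol 5.3.1 plans about 36 active and 12 placebo participants in Cohort D1, and 12 and 6 in D2. No drop-out rate or missing-data pattern for Week 40 is given.

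The Part 1 SAP's imputation variable list cannot be seen, so nothing is concluded about it.

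**The concern.** An imputation model should contain at least the covariates of the analysis it feeds. Here, missing scores are drawn as if NfL and disease duration added nothing to the participant's own baseline and observed scores. The ANCOVA then estimates an NfL effect from data in which that effect has been partly removed. The missing-at-random assumption is also not conditional on NfL.

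Missing data at Week 40 may well be related to prognosis. The plan uses imputed values after death (5.6.1), and it keeps in the analysis participants who may not continue into Part 2 (3.5). If participants with high NfL decline faster and leave earlier, their missing scores are drawn too favourably. At stake are the LS means by arm, which the plan tabulates and plots, the precision of the comparison, and in one circumstance the comparison itself.

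**Working it through.** **1. The two lists side by side**

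| Variable | Imputation list | ANCOVA |
|---|---|---|
| Treatment | yes, but constant within a by-arm run | yes |
| Riluzole/edaravone use | yes | yes |
| Endpoint's own baseline | yes | yes |
| Post-baseline scores | yes, all available | Week 40 is the outcome |
| Baseline plasma NfL | no | yes |
| Time since symptom onset | no | yes |
| Broad ALS/polyQ ALS | no | optional |

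**2. Effect on bias and precision**

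The plan gives no figure to reproduce, so the check is a simulation on assumed inputs: mean ALSFRS-R slope -1.0 point per month (SD 0.7); slope correlated 0.3 or 0.6 with NfL and 0.3 with duration; visits at Weeks 12, 24 and 40; true Week 40 difference 2.0. Imputation was by arm, with 8 imputations and 150 replicates, at ten times planned size (480 vs 180) to separate bias from noise. Monte Carlo error of the contrast is about 0.04 to 0.05.

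| NfL-slope correlation | Drop-out depends on | Missing, by arm | Contrast: omitted / included | SE ratio, omitted/included | NfL coefficient ratio, omitted/included |
|---|---|---|---|---|---|
| 0.3 | nothing | 36% / 36% | 1.95 / 1.95 | 0.599/0.592 = 1.01 | 1.731/1.933 = 0.90 |
| 0.3 | observed decline | 30% / 36% | 2.03 / 2.03 | 0.612/0.609 = 1.00 | 1.714/1.903 = 0.90 |
| 0.3 | NfL, both arms | 36% / 36% | 1.91 / 1.98 | 0.605/0.612 = 0.99 | 1.615/1.930 = 0.84 |
| 0.3 | NfL, one arm | 45% / 19% | 2.33 / 2.01 | 0.586/0.588 = 1.00 | 1.583/1.931 = 0.82 |
| 0.6 | nothing | 36% / 36% | 1.97 / 1.98 | 0.543/0.506 = 1.07 | 3.461/3.869 = 0.89 |
| 0.6 | observed decline | 31% / 36% | 1.99 / 2.00 | 0.555/0.517 = 1.07 | 3.495/3.877 = 0.90 |
| 0.6 | NfL, both arms | 36% / 36% | 2.01 / 2.01 | 0.545/0.524 = 1.04 | 3.177/3.837 = 0.83 |
| 0.6 | NfL, one arm | 45% / 19% | 2.68 / 2.01 | 0.524/0.498 = 1.05 | 3.136/3.850 = 0.81 |

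The contrast is biased only when NfL-related drop-out is confined to one arm: +0.33 at correlation 0.3 and +0.68 at 0.6. The NfL coefficient is 10 to 19% too small throughout. The standard error is 4 to 7% larger at correlation 0.6 and unchanged within about 1% at 0.3.

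**3. Planned size, 36 + 12 = 48 versus 12 + 6 = 18**

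With the arms pooled and 38 to 39% missing (also assumed), omission gave:

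- arm LS means wrong by 0.25 to 0.5 points when drop-out depended on NfL equally in both arms;
- an NfL coefficient about 20 to 25% too small and a standard error 2 to 8% larger;
- a contrast wrong by 0.4 to 0.7 points, against a standard error of about 2, only when NfL-related drop-out differed by arm.

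Adding both covariates removed these biases. A contrast bias of 0.4/2 = 0.2 to 0.7/2 = 0.35 standard errors would lower 95% coverage to Φ(1.76) - Φ(-2.16) = 94.5% and Φ(1.61) - Φ(-2.31) = 93.6%. At ten times planned size, the last row of the table gave coverage of 75% against 93% with the covariates.

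**4. Size of a by-arm model**

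Section 3.1 gives ALSFRS-R analysis visits at Weeks 4, 5, 8, 9, 12, 13, 16, 17, 20, 21, 24 and 25, then 28, 30, 32, 36 and 40: 12 + 5 = 17. Adding baseline and one or two riluzole/edaravone variables gives 19 to 20; adding NfL and duration gives 21 to 22. The delayed-start arm has about 18 planned participants.

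By-arm imputation at 48 versus 18 was unstable in simulation even with three visits. With data missing completely at random, the mean standard error was 13.0 without the two covariates and 14.5 with them, against 1.57 on complete data. The next scenario failed on a covariance matrix that was not positive definite.

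**5. The plan's own check**

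Section 5.6.1 asks for relative efficiency close to 98% or higher. With 100 imputations it is 1/(1 + λ/100), at least 1/1.01 = 99.0% for any fraction of missing information λ. It cannot detect this problem.

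**The case against.** The strongest reply is that a participant's own post-baseline scores are in the imputation model and carry much of what NfL and duration would add. This largely stands: it is why the contrast was essentially unbiased in six of the eight rows above. It is weaker for early drop-outs and for HHD, which has no scheduled assessment between Weeks 28 and 40. It did not prevent dilution of the NfL coefficient in any row.

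A second reply is that the Covariates list in 5.6.1 is introduced as applying to the statistical models generally, so the imputation model might be meant to inherit it. But the imputation paragraph gives its own list and codes treatment and riluzole/edaravone use in detail. A programmer following it would leave the two covariates out.

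A reader might infer that the Week 40 treatment differences are distorted as a matter of course, or that the imputation ignores the main prognostic factor. The documents support neither. They adjust for NfL but nowhere rank it as the main prognostic factor, and they describe no drop-out pattern that differs by arm.

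The stakes are also limited. The study was stopped early for lack of effect, the report is abbreviated (Section 1), and the stated objective is long-term safety (2.1). That lowers the weight of the point, but the ANCOVA and its p-values are still planned.

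**Conclusion.** The mismatch is certain from the text and affects all three clinical function endpoints. Its effect depends on why data are missing. If drop-out is unrelated to NfL or related to it equally in both arms, the Early-start versus Delayed-start contrast is essentially unbiased. Under NfL-related drop-out, the arm LS means are biased by about 0.25 to 0.5 points, the NfL adjustment is diluted and the standard error is somewhat larger when NfL is strongly related to slope. The contrast itself can be biased, by 0.4 to 0.7 points at planned size, if NfL-related drop-out differs by arm.

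Every one of these sizes rests on assumed slopes, correlations and drop-out. The simulations also used one continuous score, whereas the plan imputes four ALSFRS-R domains separately and resets out-of-range values; and the planned-size results pool the arms, which the plan does not do. This is a model mismatch worth correcting, not evidence that the reported comparison is wrong.

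**What to change.** In the multiple-imputation text of 5.6.1, add baseline plasma NfL and time since symptom onset, in the same form as in the ANCOVA, to the variable list for each ALSFRS-R domain, SVC and HHD. If the optional broad ALS/polyQ ALS term is used in the ANCOVA, include it as well.

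In the same sentence, replace imputation by treatment group with one model across both arms, using the treatment indicator that the section already codes. About 66 planned participants then support the model instead of 18, and the listed treatment variable has a function.

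Do not make room by dropping Weeks 5, 9, 13, 17 and 21 as off-schedule. They are scheduled ALSFRS-R visits (Days 36, 64, 92, 120 and 148), and SVC and HHD are not collected then. Dropping them from a by-arm ALSFRS-R model would still leave 12 visits + baseline + 1 to 2 riluzole/edaravone variables + 2 new covariates = 16 to 17 variables for about 18 delayed-start participants.

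The cost is a short SAP amendment using variables the ANCOVA already requires, a slightly larger imputation model, and an assumption of common covariances across arms.
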